3.2.1.3. Recommended Phase 2 Dose (RP2D) Definition

The RP2D is the dose chosen for further study in Phase 2 based on the Phase 1b results. RP2D dose selection will be based on the entirety of the safety, efficacy, and clinical pharmacology data using an integrated quantitative approach. The RP2D may be the MTD unless one or more of the following suggest an alternate dose below the MTD would be preferable:

- a. clinically significant anti-tumor effect (complete response [CR], partial response [PR], or prolonged stable disease [SD]) occurs below the MTD, in which case a clinically active dose level may be selected as the RP2D;
- b. the MTD is not achieved, in which case the highest dose level administered may become the RP2D; or
- c. toxicities observed beyond the DLT evaluation period (Cycle 1) require selecting the RP2D below the MTD level.

Once the MTD of repotrectinib in combination with trametinib has been determined, the RP2D will be determined at or below the MTD. At least 6 subjects will be treated at the RP2D prior to proceeding into the Phase 2 portion of the study. Additional subjects may be added at a dose level to gather more safety, PK, and efficacy data.

3.2.1.4. Follow-Up After a Dose-Limiting Toxicity

When treatment is interrupted due to a DLT, the subject must be followed at least once a week for 4 weeks, and subsequently at a maximum interval of 4 weeks, until resolution or stabilization of the event, whichever comes first.

3.2.1.5. Safety Review Committee

For the Phase 1b portion of the study, a Safety Review Committee comprised of at minimum the Sponsor Medical Monitor and study Investigators will review all relevant safety and other relevant clinical data and will provide recommendations on the following:

- Confirmation of DLTs
- Dose escalation decisions within the dose escalation portion
- Selection of RP2D

3.3. Phase 2 Expansion Study Design

Once the MTD/RP2D of repotrectinib in combination with trametinib has been determined, approximately 50 subjects will be enrolled into the Phase 2 expansion portion. The Phase 2

portion is designed to explore the anti-tumor efficacy and safety of repotrectinib in combination with trametinib for the treatment of patients with locally advanced or metastatic NSCLC harboring a *KRAS*^{G12D} mutation.

An interim futility analysis of the ORR will be performed after approximately 15 subjects are evaluable for tumor response. If ≤ 2 responders (confirmed CR or PR) are observed from 15 evaluable subjects, the expansion cohort will be stopped for futility. If ≥ 3 responders are observed, this cohort may continue depending on the overall benefit and risk assessment at the interim analysis.

Tumor assessments will include all known or suspected disease sites. All radiographic efficacy endpoints will be assessed using RECIST v1.1. Intracranial responses will be assessed by modified RECIST v1.1. For all tumor assessments, the imaging modality used at baseline should be the same modality used throughout the study.

Safety will be monitored *via* laboratory assessments, physical examinations, electrocardiograms (ECG), vital signs, and TEAEs according to CTCAE v5.0. PK data will also be collected. In addition, safety will be monitored by a Safety Review Committee comprised of at minimum the Sponsor Medical Monitor and study Investigators to review all relevant safety and other relevant clinical data. The following study stopping rules will apply for the Phase 2 portion of the study:

- Any death (other than disease progression) that is at least possibly related to the study agent.
- Occurrence of two or more Grade 4 events that are at least possibly related to the study agent.

3.4. Study Duration

Subjects will remain on study treatment until confirmed radiographic disease progression, development of unacceptable toxicity, or withdrawal of consent. There is no limit to the number of cycles of treatment with repotrectinib or trametinib.

For subjects discontinuing the study treatment due to documented radiographic progression, obtain survival status via phone call or medical chart review, including information about subsequent anticancer therapies (including best response) every 3 months until death, loss of follow-up, or withdrawal of consent, whichever comes first. For subjects discontinuing the study treatment prior to documented radiographic progression, tumor assessments should continue on the schedule approximately every 2 months or at the current scan interval at the time of treatment discontinuation until radiographic evidence of disease progression, the start of a subsequent anticancer therapy, or decision to no longer treat (e.g., supportive care only), whichever is first.

3.5. Dose Modifications

For subjects who experience a DLT, dose adjustments are permitted if it is considered in the best interest of the subject to continue therapy after discussing with the Sponsor's Medical Monitor. Dose modification guidelines for repotrectinib are described in the Dose Modification Guidelines for Adverse Events table ([Table 4](#)). Dose reductions for repotrectinib will follow the dose levels provided in [Table 2](#). The guidelines provided in the label for trametinib should be referenced and

followed to manage toxicities associated with trametinib (i.e., see Table 2 in [Mekinist® \[trametinib\] USPI 2020](#)).

If toxicity is clearly attributed to one drug based on the known toxicity profile then one drug may be modified while the other is continued at the current dose. If the toxicity cannot clearly be attributed to one drug, then a dose modification for both drugs will be implemented according to the Dose Modification Guidelines for Adverse Events table for repotrectinib ([Table 4](#)) and per label for trametinib (see Table 2 in [Mekinist® \[trametinib\] USPI 2020](#)).

Subjects who cannot be re-treated with study drug should have weekly follow-ups that include a physical examination, vital signs including weight, Eastern Cooperative Oncology Group (ECOG) performance status (PS), ECGs, and assessment of AEs and concomitant medication. Following a DLT or toxicity, hematology, renal, and liver function tests (LFTs) should be performed as appropriate.

If a subject requires a dose delay of > 28 days from the intended day of the next scheduled dose of study drugs, then the subject must be discontinued from the study. If a subject requires more than two dose reductions for either agent, then the subject must be discontinued from the study.

Subjects who discontinue from the study for a study drug-related AE or a grade 3 or higher abnormal laboratory value must be followed as described in [Section 7.3](#).

3.5.1. Dose Interruptions and Delays

Dose interruptions may occur in the event of a treatment-related toxicity or a non-treatment-related issue (e.g., elective surgery). If toxicity is clearly attributed to one drug based on the known toxicity profile then one drug may be interrupted while the other is continued. If the toxicity cannot clearly be attributed to one drug, then dose interruption for both drugs will be implemented.

Appropriate follow-up assessments should be done until adequate recovery occurs as assessed by the Investigator. Criteria required before treatment can resume for repotrectinib are described in the dose modification guidelines for adverse events table ([Table 4](#)). The guidelines provided in [Table 4](#) are general guidelines for dose modifications due to toxicities that may arise from repotrectinib. The guidelines provided in the label for trametinib should be referenced and followed to manage toxicities (i.e., see Table 2 in [Mekinist® \[trametinib\] USPI 2020](#)).

Doses may be held as needed until toxicity resolution. Depending on when the AE is resolved, a treatment interruption may lead to the subject missing all subsequent planned doses within that same cycle or even to delay the initiation of the subsequent cycle.

If a treatment delay results from worsening of hematologic or biochemical parameters, the frequency of relevant laboratory assessments may be increased as clinically indicated.

If the AE that led to the treatment interruption recovers within the same cycle, then re-dosing in that cycle is allowed. Doses omitted for toxicity are not replaced within the same cycle. The need for a dose reduction at the time of treatment resumption should be based on the criteria defined in [Table 4](#) unless otherwise agreed to following discussion between the Investigator and the Medical Monitor.

In the event of a treatment interruption for reasons other than treatment-related toxicity (e.g., elective surgery) lasting \geq 14 days, treatment resumption must be discussed with the Medical Monitor.

All study visits (visit date calculations) are based off the Cycle 1 Day 1 visit date, regardless of dose interruptions, and evaluations are to be performed according to the Schedule of Activities ([Table 1](#)). Every effort should be made to maintain the tumor assessments scheduling as described in the Schedule of Activities.

Table 4: Repotrectinib Dose Modification Guidelines for Adverse Events (CTCAE v5.0)

Toxicity	CTCAE Grade 1*	CTCAE Grade 2*	CTCAE Grade 3	CTCAE Grade 4
Hematologic	Continue at same dose level.	Continue at same dose level.	Withhold dose until toxicity is grade ≤ 2 , or has returned to baseline, then resume treatment at the same dose level or reduce by one dose level ^{1,2} as per the Investigator's discretion. Grade 3 lymphopenia without other dose-limiting events (e.g., opportunistic infection) may continue study treatment without interruption.	Withhold dose until toxicity is grade ≤ 2 , or has returned to baseline, reduce the dose by one dose level ^{1,2} and resume treatment. Grade 4 lymphopenia without other dose-limiting events (e.g., opportunistic infection) may continue study treatment without interruption.
Non-Hematologic excluding dizziness, ataxia, and paresthesia	Continue at same dose level.	Continue at same dose level. For prolonged or intolerable CNS toxicity, withhold dose until toxicity is grade ≤ 1 or has returned to baseline, then reduce by one dose level ^{1,2} and resume treatment.	Withhold dose until toxicity is grade ≤ 1 or has returned to baseline.	Withhold dose until toxicity is grade ≤ 1 or has returned to baseline, then reduce by one dose level ^{1,2} and resume treatment; or discontinue treatment as per the Investigator's discretion.
ILD/Pneumonitis (occurred in the absence of disease progression, pulmonary embolism, positive cultures or radiation effect)	Asymptomatic, radiographic findings only: No need for dose adjustment. Initiate appropriate monitoring. Symptomatic: Withhold current dose until toxicity has returned to baseline. Rule out infection and consider initiating treatment with corticosteroids. Then resume treatment at the same dose. Discontinue permanently if pneumonitis recurs or if failure to recover after 28 days	Withhold current dose until toxicity has returned to baseline. Rule out infection and consider initiating treatment with corticosteroids. Then resume treatment at one dose level lower. Discontinue permanently if pneumonitis recurs or if failure to recover after 28 days of study treatment hold and steroid treatment.	Discontinue treatment permanently.	Discontinue treatment permanently.

Toxicity	CTCAE Grade 1*	CTCAE Grade 2*	CTCAE Grade 3	CTCAE Grade 4
	of study treatment hold and steroid treatment.			
AST or ALT elevation	Continue at same dose level.	Continue at same dose level. Withhold current dose if concurrent CTCAE grade ≥ 2 total bilirubin elevation ($> 1.5 \times$ ULN).	Withhold current dose until resolves to Grade ≤ 1 .	Discontinue treatment permanently.
Prolonged QTc	Assess electrolytes and concomitant medications. Correct any electrolyte abnormalities, or hypoxia. Continue at the same dose level.	Assess electrolytes and concomitant medications. Correct any electrolyte abnormalities, or hypoxia. Continue at the same dose level.	Withhold dose Assess electrolytes and concomitant medications. Correct any electrolyte abnormalities, or hypoxia. Upon recovery to grade ≤ 1 : if no other cause for QTc prolongation is found or is considered drug-related resume treatment at 1 dose level lower.	Discontinue treatment.
Dizziness, ataxia, or muscular weakness	Continue at same dose level.	Withhold current dose until toxicity is grade ≤ 1 or has returned to baseline OR reduce by 1 dose level immediately ^{1,2}	Withhold dose until toxicity is grade ≤ 1 or has returned to baseline, then reduce by 1 dose level ^{1,2} and resume treatment	Withhold dose until toxicity is grade ≤ 1 or has returned to baseline, then reduce by 1 dose level ^{1,2} and resume treatment; or discontinue treatment as per the Investigator's discretion after discussion with Medical Monitor.

Toxicity	CTCAE Grade 1*	CTCAE Grade 2*	CTCAE Grade 3	CTCAE Grade 4
Weight gain	Continue at same dose level. Implement effective weight management strategy (dietary advice from a nutritionist and food intake counseling).	Dose interrupt or dose reduce ^{1,2} , if required.	Dose interrupt or dose reduce ^{1,2} , if required.	Not applicable.

Abbreviations: ALT = alanine aminotransferase; AST = aspartate aminotransferase; CNS = central nervous system; CTCAE = Common Terminology Criteria for Adverse Events, v5.0; ILD = interstitial lung disease; QTc = QT interval corrected for heart rate; ULN = upper limit of normal.

*Cycle will not be extended to cover for the missing doses. In cases where no specific dose adjustments for CTCAE Grade 1 or Grade 2 treatment-related toxicity are provided, Investigators should always manage their subjects according to their medical judgment, which may include dose reduction or interruption based on the particular clinical circumstances.

¹If subjects are assigned to the Dose Level -3 dose level, further dose reductions will not be implemented. Subjects will be discontinued if a dose reduction is required.

²Dose reductions for repotrectinib will follow the dose levels provided in [Table 2](#).

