Other AEs	
 Grade 3 electrolyte disturbances that require hospitalization Grade 4 electrolytes abnormalities Grade ≥ 3 AE, persisting after optimal treatment with standard medical therapy except for the exceptions noted below under “Exceptions to DLT criteria” In view of the Investigators and Sponsor, any other unacceptable toxicity encountered
Exceptions to DLT criteria	
 Grade 3 elevations in ALP Grade 3 electrolytes abnormalities that are adequately managed by IV or PO supplementation as evidenced by an improvement to grade ≤ 1 within 3 days Grade 3 fatigue which resolves to grade ≤ 1 in ≤ 7 days Isolated grade 3 laboratory abnormalities that are not associated with clinical sequelae and are corrected with supplementation/appropriate management within 72 hours of their onset Grade 3 dizziness which resolves to grade ≤ 1 within ≤ 7 days

Abbreviations: AE = adverse event; ALP = alkaline phosphatase; ALT = alanine aminotransferase; ANC = absolute neutrophil count; AST = aspartate aminotransferase; CTCAE = Common Terminology Criteria for Adverse Events, v5.0; DLT = dose-limiting toxicity; IV = intravenous; PO = per os (by mouth); ULN = upper limit of normal.

Toxicities clearly related to disease progression or intercurrent illness will not be considered DLTs.

In addition, clinically important or persistent toxicities not included in the above criteria may be considered a DLT following review by the Sponsor and study Investigators. All DLTs should represent a clinically significant shift from baseline. These will be evaluated according to National Cancer Institute CTCAE v5.0.

To fully characterize the safety of repotrectinib in combination with trametinib, subjects who are discontinued from treatment before completing the DLT evaluation period (28 days, Cycle 1) due to disease progression or other event unrelated to study drugs, or who did not adequately complete the PK evaluations within Cycle 1, may be replaced.

Dose re-escalation for subjects with DLTs is not allowed in the Phase 1b portion of the study. Subjects experiencing a DLT may resume dosing at the next lower dose level (if applicable) once adequate recovery is achieved.

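### Table 4 has no row for paresthesia and puts muscular weakness in two rows whose Grade 2 instructions conflict

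*Combined protocol and SAP*

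**What the plan says.** Table 4 has seven rows: hematologic, general non-hematologic, ILD/pneumonitis, AST or ALT elevation, prolonged QTc, a specific neuromuscular row, and weight gain. The general row is titled "Non-Hematologic excluding dizziness, ataxia, and paresthesia". The specific row is titled "Dizziness, ataxia, or muscular weakness".

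The asterisk note under the table gives a fallback to medical judgment, limited to the two lowest grades: "In cases where no specific dose adjustments for CTCAE Grade 1 or Grade 2 treatment-related toxicity are provided".

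Section 3.5.1 relies on the table for two decisions. On recovery: "Criteria required before treatment can resume for repotrectinib are described in the dose modification guidelines for adverse events table". On dose: "The need for a dose reduction at the time of treatment resumption should be based on the criteria defined in" Table 4, unless the Investigator and the Medical Monitor agree otherwise after discussion. The same section describes the table as general guidelines.

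Other text applies whatever the row:
- Section 3.5.1: "Doses may be held as needed until toxicity resolution", with recovery judged by the Investigator.
- Section 3.5: participation ends "If a subject requires a dose delay of > 28 days from the intended day of the next scheduled dose of study drugs", or after more than two dose reductions of either agent.
- Section 3.2.1.1, for Phase 1b: "Subjects experiencing a DLT may resume dosing at the next lower dose level (if applicable) once adequate recovery is achieved".

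**The concern.** The two titles look as if they were meant to be complementary, with the events removed from the general row being those taken up by the specific row. They are not. Muscular weakness stands where paresthesia would be expected, so one event has no row and another has two.

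Sites can expect to meet paresthesia. Section 1.5 lists it among the common monotherapy events, and the neurological examination in Section 6.6 checks for it by name. Exclusion criterion 9 bars subjects with Grade 2 or higher paresthesia at entry, so a Grade 2 or higher event on treatment is new or a worsening. At stake is whether a site with a severe case can find the instruction that Section 3.5.1 says is in the table.

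**Working it through.** The plan states no figure on this point, so the check is a comparison of text.

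**Step 1. Which row covers each event?**

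| Event | Removed from general row? | Named in specific row? | Rows that apply |
|---|---|---|---|
| Dizziness | yes | yes | 1 |
| Ataxia | yes | yes | 1 |
| Paresthesia | yes | no | 0 |
| Muscular weakness | no | yes | 2 |

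None of the other five rows could take paresthesia.

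**Step 2. Does the choice of row matter?**

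| Grade | General row | Specific row |
|---|---|---|
| 1 | continue | continue |
| 2 | continue; hold then reduce only for prolonged or intolerable CNS toxicity | hold to Grade 1 or lower or baseline, or reduce one level at once |
| 3 | hold to Grade 1 or lower or baseline; no resumption dose stated | same hold, then reduce one level |
| 4 | same hold, then reduce one level, or discontinue at Investigator discretion | as general row, with Medical Monitor discussion before discontinuing |

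The rows differ at Grades 2 and 3. For muscular weakness this is a direct conflict at Grade 2. For paresthesia, a site cannot pick a row by guessing without also picking a policy.

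**Step 3. What is left for paresthesia?**

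- Grades 1 and 2: medical judgment, under the asterisk note.
- Grade 3 or higher: the asterisk note does not reach it. The general hold text, the 28-day and two-reduction limits and the Medical Monitor route still apply. None of them states a recovery grade.
- Resumption dose at Grade 3 or higher: one level lower after a Phase 1b DLT. For any other event, including all of Phase 2, no text fixes it.

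**Step 4. How many subjects?**

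Section 1.5 gives paresthesia of any grade in 25.4% of 185 monotherapy subjects: 0.254 × 185 = 47. It gives no split by grade, so the number at Grade 3 or higher cannot be derived, and zero is compatible with the documents.

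**The case against.** The strongest reply is that the protocol still works without the row. Table 4 is only a set of general guidelines, the Investigator and Medical Monitor may agree a different dose at resumption, and dosing can always be held. This stands, and a reader should not infer that severe paresthesia is unmanaged. The gap is narrower: the table lacks the criteria that Section 3.5.1 says it contains.

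A reader might infer that the missing row is what lets sites resume at different doses. The documents do not support that. The general row states no resumption dose for any Grade 3 non-hematologic event, the AST/ALT row states none at Grade 3, and the hematologic row leaves Grade 3 to the Investigator. Measured against the general row, Grade 3 paresthesia loses only an explicit hold and recovery grade.

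A reader might also apply the monotherapy rate to the planned total of 24 + 50 = 74 to 30 + 50 = 80 subjects and conclude that about 19 to 20 are affected (0.254 × 74 = 18.8; 0.254 × 80 = 20.3). That counts all grades, and the asterisk note covers Grades 1 and 2. It also assumes that the monotherapy rate holds with trametinib.

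For muscular weakness, one can answer that a named row normally overrides a general one. That is a sensible reading, but the table does not say so, and it does not help paresthesia, which no row names.

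**Conclusion.** The point holds as a minor fault in a safety instruction. Paresthesia has no row; muscular weakness has two, which conflict at Grade 2. The practical gap is Grade 3 or higher paresthesia: no recovery grade is set in either phase, and no resumption dose is set except after a Phase 1b DLT. How often this will arise is unknown, and it may never arise. The conclusion rests on the row titles as printed. Both are complete phrases, and nothing suggests text lost in conversion. No endpoint, sample size or error rate is affected.

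A reader might go further and infer that the Day 15 step to 160 mg BID (Table 2, footnote a) contradicts Table 4, because that footnote bars only unmanageable Grade 2 or higher dizziness, ataxia or paresthesia. The documents do not support this. The step is permissive and follows an Investigator safety assessment, and for Grade 2 dizziness or ataxia Table 4 already directs a hold or reduction. The two can be applied together. At most the order of precedence is unstated.

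**What to change.** Retitle two rows of Table 4 so that the specific row lists dizziness, ataxia, paresthesia and muscular weakness, and the general row excludes the same four. Each event then has exactly one row. The specific row is a reasonable home for paresthesia because Table 2 footnote a and the monotherapy step-up criterion in Section 1.5 group it with dizziness and ataxia.

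That grouping does not prove what the sponsor intended. If a Grade 2 hold or reduction for paresthesia is not wanted, remove paresthesia from the general row's exclusion and add muscular weakness there instead. Paresthesia then follows the general row, and muscular weakness sits only in the specific one.

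Either option changes two row titles and adds no visits or data. The first has three consequences to accept knowingly:
- Grade 2 paresthesia moves from judgment to hold or reduce.
- At Level -3, Grade 3 paresthesia means discontinuation, because footnote 1 to Table 4 allows no further reduction there.
- At Levels 1 and -2, a one-level reduction (to -2 and -3 respectively) lowers only trametinib. Repotrectinib stays at 120 mg QD, the lowest dose in Table 2. This is a live case: Appendix 2 records that the Safety Review Committee recommended de-escalation to Level -2.

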8.2.5.6. Abnormal Liver Function Tests

Abnormal values in aspartate transaminase (AST) and/or alanine transaminase (ALT) levels concurrent with abnormal elevations in total bilirubin level that meet the criteria outlined below in the absence of other causes of liver injury are considered potential cases of drug-induced liver injury (potential Hy's Law cases) and should always be considered important medical events.

The threshold of laboratory abnormalities for a potential case of drug-induced liver injury depends on the subject's individual baseline values and underlying conditions. Subjects who present with the following laboratory abnormalities should be evaluated further to definitively determine the etiology of the abnormal laboratory values:

- Subjects with AST or ALT and total bilirubin baseline values within the normal range who subsequently present with AST or ALT values $> 3 \times$ ULN concurrent with a total bilirubin value $> 2 \times$ ULN with no evidence of hemolysis and an ALP value $\leq 2 \times$ ULN or not available.
- For subjects with preexisting ALT OR AST OR total bilirubin values above the ULN, the following threshold values should be used in the definition mentioned above:

- For subjects with preexisting AST or ALT baseline values above the normal range, AST or ALT value \geq 2 times the baseline values and $\geq 3 \times$ ULN, or $\geq 8 \times$ ULN (whichever is smaller).
- Concurrent with
 - For subjects with preexisting values of total bilirubin above the normal range: Total bilirubin increased from baseline by an amount of $\geq 1 \times$ ULN or if the value reaches $\geq 3 \times$ ULN (whichever is smaller).

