The subject should return to the investigational site and be evaluated as soon as possible, preferably within 48 hours from awareness of the abnormal results. This evaluation should include laboratory tests, detailed history and physical assessment. The possibility of hepatic neoplasia (primary or secondary) should be considered. In addition to repeating measurements of AST and ALT, laboratory tests should include albumin, creatine kinase, total bilirubin, direct and indirect bilirubin, gamma-glutamyl transferase, prothrombin time (PT)/international normalized ratio (INR), ALP, and total bile acids and acetaminophen drug and/or protein adduct levels. A detailed history, including relevant information, such as review of ethanol, acetaminophen, recreational drug and supplement consumption, family history, occupational exposure, sexual history, travel history, history of contact with a jaundiced person, surgery, blood transfusion, history of liver or allergic disease, and work exposure, should be collected. Further testing for acute hepatitis A, B, or C infection and liver imaging (e.g., biliary tract) may be warranted. All cases confirmed on repeat testing as meeting the laboratory criteria defined above, with no other cause for LFT abnormalities identified at the time should be considered potential Hy's Law cases irrespective of availability of all the results of the investigations performed to determine etiology of the abnormal LFTs. Such potential Hy's Law cases should be reported as SAEs.

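### From Cycle 2 of Phase 1b and throughout Phase 2, Table 4 leaves restart terms incomplete for Grade 2–3 AST/ALT with raised bilirubin, and Section 8.2.5.6 supplies no dosing rule

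*Combined protocol and SAP*

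**What the plan says.** **Section 8.2.5.6.** For a subject with normal baseline values, the trigger is AST or ALT above 3 × ULN "concurrent with a total bilirubin value" above 2 × ULN, with no hemolysis and ALP at most 2 × ULN or unavailable. In the absence of another cause these events "should always be considered important medical events". The subject is to be evaluated, preferably within 48 hours. Cases confirmed on repeat testing "with no other cause for LFT abnormalities identified at the time should be considered potential" Hy's Law cases, and potential Hy's "Law cases should be reported as SAEs". Nothing in the section tells the site to hold, stop or restart a study drug.

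**Section 3.5.1 and Table 4.** The text names Table 4 as the source of repotrectinib restart criteria. Table 4 also governs dose reduction at resumption, unless the Investigator and Medical Monitor agree otherwise. Trametinib follows its label. In the AST/ALT row:
- Grade 1 continues at an unchanged dose.
- Grade 2 continues too, with the added instruction "Withhold current dose if concurrent CTCAE grade ≥ 2 total bilirubin elevation" (above 1.5 × ULN).
- Grade 3 reads "Withhold current dose until resolves to Grade ≤ 1".
- Grade 4 is a permanent stop.

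The general non-hematologic row continues Grade 2 events and holds Grade 3 events until Grade ≤ 1 or baseline.

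**Section 3.2.1.1 and Table 3.** Grade ≥ 2 bilirubin together with Grade ≥ 2 ALT or AST is a hepatic DLT in Cycle 1 of Phase 1b. The section adds: "Subjects experiencing a DLT may resume dosing at the next lower dose level (if applicable) once adequate recovery is achieved".

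**The concern.** The protocol gives the combined elevation special status in the safety-reporting section, but that status does not carry over to dosing. A site looking for what to do with repotrectinib finds an open-ended hold in the Grade 2 AST/ALT cell. In the Grade 3 cell it finds a release condition that ignores bilirubin. Neither cell gives a restart dose, and no section requires a permanent stop for a confirmed potential Hy's Law case unless AST/ALT is Grade 4.

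Other Table 4 cells show that fuller instructions were feasible. Grade 2 pneumonitis has a recovery condition, a lower restart dose and a permanent stop on recurrence. Grade 3 drug-related QTc prolongation has a recovery grade and a lower restart dose.

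What is at stake is subject safety and consistency between sites, in a combination with little clinical experience: the summary of changes refers to two patients treated at Dose Level 1. ORR, the DLT rate, the MTD and the sample size are not in question.

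**Working it through.** The plan states no figure on this point. The check maps the Section 8.2.5.6 event onto the Table 4 cells, for subjects with normal baseline values.

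**Inputs (Table 3 cut-offs; Tables 3 and 4 both use CTCAE v5.0).** AST/ALT: Grade 2 is above 3 × ULN and Grade 3 above 5 × ULN. Bilirubin: Grade 2 is above 1.5 × ULN and Grade 3 above 3 × ULN. Grade ≤ 1 therefore means AST/ALT at most 3 × ULN and bilirubin at most 1.5 × ULN. A case with bilirubin above 2 × ULN always meets the Grade ≥ 2 bilirubin condition.

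**Mapping from Cycle 2 of Phase 1b, and in all of Phase 2**

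| AST/ALT | Bilirubin | Hold ends when | Restart dose | Permanent stop |
|---|---|---|---|---|
| Grade 2 | Grade 2 | not stated | not stated | none |
| Grade 3 | Grade 2 | AST/ALT Grade ≤ 1; bilirubin not mentioned | not stated | none |
| Grade 2 or 3 | Grade 3 | general row adds bilirubin Grade ≤ 1 or baseline | not stated | none |
| Grade 4 | any | not applicable | not applicable | yes |

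In Cycle 1 of Phase 1b every row of this table is a DLT. For the rows without a stop, resumption is one dose level lower after adequate recovery, which has no numeric definition.

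**Grade 2 cell, two readings.** Read literally, the hold is conditional on bilirubin. When bilirubin reaches 1.5 × ULN the condition lapses, and the cell's default (same dose) applies with AST/ALT anywhere up to 5 × ULN. Read with the general Section 3.5.1 sentence that doses can be held until the toxicity resolves, the hold lasts longer, to a value the plan does not give.

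**Required falls before restart** (1 − target/observed, multiples of ULN)
- Isolated ALT 5.1 (Grade 3): 1 − 3/5.1 = 41.2%.
- ALT 4.9 with bilirubin 2.9, literal reading: bilirubin 1 − 1.5/2.9 = 48.3%; ALT 0%.
- The same case, if a site takes resolution to mean both values at Grade ≤ 1: bilirubin 48.3%; ALT 1 − 3/4.9 = 38.8%.
- ALT 6 with bilirubin 2.9 (Grade 3 cell): ALT 1 − 3/6 = 50.0%; bilirubin 0%, because bilirubin of 2.9 is Grade 2 and the general row continues it.

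The last case does not depend on how the Grade 2 cell is read. In the Grade 2 case, the required ALT fall ranges from 0% to 38.8% according to the reader.

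**The case against.** A reader might infer that Table 4 gives the combined elevation no permanent stop, restart value or restart dose at all. The documents do not support that. The Section 8.2.5.6 event has no upper AST/ALT limit, and Grade 4 AST/ALT is stopped permanently whatever the bilirubin. Grade 3 AST/ALT has a restart value for AST/ALT. Grade 3 bilirubin is held by the general row, and a Cycle 1 case in Phase 1b resumes only one level lower.

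A reader might also infer that the protocol allows restart at full dose with AST/ALT unchanged. That is one of two readings of the Grade 2 cell. Section 3.5.1 speaks of resolution and adequate recovery, and ALT at 4.9 × ULN is hard to call recovery from a combined liver event. The footnote to the Grade 1 and 2 columns leaves cases without a specific adjustment to medical judgment, including dose reduction.

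Oversight exists too. SAEs reach the Medical Monitor within 24 hours (Section 8.1.1), the sponsor may obtain further details for its own medical assessment (Section 8.4.2), and the Safety Review Committee reviews Phase 2 safety. A delay beyond 28 days requires discontinuation (Section 3.5).

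All of this stands as a limit on the point. It does not close the gap. These provisions allow stricter handling without requiring it, reporting is not a dosing rule, and the 28-day limit does not govern an earlier restart. A permanent stop is also a design judgment: no text in the plan sets it as the standard below Grade 4 AST/ALT.

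**Conclusion.** The point holds in a limited form. The gap is Grade 2–3 AST/ALT with raised bilirubin, from Cycle 2 of Phase 1b and throughout Phase 2. Within it:
- the Grade 2 cell lacks a restart value and a restart dose;
- the Grade 3 cell lacks a bilirubin condition and a restart dose;
- a confirmed potential Hy's Law case has no required stop.

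The same combination in Cycle 1 of Phase 1b would resume only at a lower dose level, and the plan gives no reason for the difference.

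The 41%, 48% and 50% falls are worked examples, not estimates of what subjects will experience, and the 0% ALT figure rests on the literal reading of the Grade 2 cell. The mapping assumes normal baseline values and the Table 3 cut-offs. The frequency of such cases is not in the documents. The trametinib label was not available, so the conclusion concerns repotrectinib only.

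**What to change.** Amend the AST/ALT row of Table 4, or add a row beneath it:

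1. For Grade 2–3 AST/ALT with concurrent Grade ≥ 2 bilirubin, hold repotrectinib until both AST/ALT and bilirubin are Grade ≤ 1 or baseline, then resume one dose level lower. This matches the lower dose in the Cycle 1 DLT rule and adds the recovery value that rule lacks.
2. For a case meeting Section 8.2.5.6, confirmed on repeat testing with no other cause, discontinue repotrectinib permanently. Handle trametinib by its label and the attribution rules in Section 3.5.
3. Add a cross-reference from Section 8.2.5.6 to Table 4.

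Under item 1, a subject with ALT 6 and bilirubin 2.9 × ULN and another cause identified would need falls of 50.0% and 48.3% with normal baselines, instead of 50.0% and 0%.

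The cost is a wording amendment, with no added subjects, visits or tests, since the work-up is already required. There are two consequences to accept openly. A confirmed case loses repotrectinib even if the tumor is responding, so the sponsor should state whether the clinical-benefit exception in Section 7.3 applies. A subject at Dose Level -3 who needs a reduction is discontinued under Table 4 footnote 1, so for that subject item 1 also means stopping.
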